2. STUDY OBJECTIVES

Primary and secondary objectives

The primary objective of this study is to compare the efficacy of gabapentin enacarbil 600 mg BID taken 1 day pre-op and approximately 2 hours before the surgery and restarted within 6 hours of completion of surgery and then 3 days post-operative versus placebo in reducing the use of opiates and/or pain scores in post-hip and knee arthroplasty surgery patients with spinal anesthesia.

Using a randomized design and blinded assessments, our goal is to determine whether Gabapentin enacarbil when used as a modality of pre-emptive analgesia decreased opioid consumption and/or decreased pain scores in hip and knee arthroplasty surgery.

The proposed research will have the following aims:

Primary objectives include:

Primary Aim 1: To assess whether gabapentin enacarbil decreases pain and/or opioid requirements after hip or knee surgery.

Hypothesis: Patients received gabapentin enacarbil will have less pain scores and/or less opioid consumption during the initial 72 hours after hip or knee surgery compared to patients who received placebo, and not worse on either outcome.

Secondary objectives include:

Secondary Aim 1: To assess whether gabapentin enacarbil decreases the incidence of persistent incisional pain three months after surgery when used as a modality of pre-emptive analgesia.

Hypothesis: Gabapentin enacarbil decreases the persistence of incisional pain three months after surgery.

Secondary Aim 2: To evaluate whether gabapentin enacarbil decreases nausea and vomiting during the initial 72 post-operative hours.

Hypothesis: The incidence of postoperative nausea and vomiting is reduced in patients given gabapentin enacarbil during the initial 72 hours after hip and knee replacement surgery.

Secondary Aim 3: To evaluate whether gabapentin enacarbil reduces the duration of hospitalization.

Hypothesis: The duration of hospitalization after knee or hip arthroplasties is reduced in patients given gabapentin enacarbil.

Secondary Aim 4: To evaluate whether gabapentin enacarbil will improve patient's satisfaction.

Hypothesis: Patients are more satisfied with the pain and quality of life after taking gabapentin enacarbil compared to placebo, as assessed using the quality of recovery score (QoR-15).

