4.5 Data Collection and Follow Up for Withdrawn Subjects

1. Data obtained from electronic medical records will include: operation time, surgery type, intraoperative opioid consumption, postoperative opioid consumption in PACU and in ward, breakthrough pain medication requirements, pain scores in PACU and ward, requirement of antiemetics for nausea and vomiting, requirement of antihistaminic medications, requirement of laxatives for constipation, ambulation time, flatus, ileus, bowel movements, length of stay and any side effects or complications.
2. Preoperative and postoperative laboratory data including but not limited to renal function results will also be collected from electronic medical records. Patient functionality will also be recorded including, bathing, toileting, walking and moving.
3. Patients will be evaluated for pain (using numerical rating scale) (NRS) once in the PACU (Post-Anesthesia Care unit) every 15 minutes during the initial first hour after surgery and then on the first, second and third post-operative morning. Amount of opioids used, rescue anti-emetics used, nausea, vomiting and pain scores will be documented in EPIC.
4. With all study patients, post-operative pain at rest will be collected and reflected using the Numerical rating scale (NRS) pain scale. The patient is asked to rate the pain within (0-10), with zero indicating no pain and 10 indicating the worst imaginable pain.
5. Pain will be evaluated both at rest and after exercise as per physiotherapy protocol. This would be a global assessment of pain since the last assessment.
6. Patient satisfaction with their pain treatment will be questioned after 72 hours or at discharge whichever comes first using 0-5 scales and we will also use QoR-15 score to formally evaluate quality of recovery. The QoR-15 score is a validated scoring system allows quantification of patient's early postoperative health status, which is also a

description of quality of recovery. The QoR-15 score will be performed on 72 hours post op or at discharge whichever comes first.

7. Patients will be contacted by telephone at 3 months after surgery and queried regarding presence of new pain since surgery and its interference with activities of daily living. Phone call is made with the purpose of checking for pain conversion from acute to chronic and to check for any adverse event.

5. STUDY DRUG (or Device, Biologic, Treatment)

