⁵ Physical evaluations include monitoring vital signs, checking general wellbeing and pain evaluation both pre-operatively and post-operatively. Patients will be evaluated by orthopedic surgeons pre-operatively and post-operatively as per their protocol. Physical therapy will evaluate the patients for pain, mobility and strength as per physical therapy protocol. Physical therapy and orthopedic surgeons will record and document their findings in EPIC.

⁶ Patients will be monitored throughout their stay in the hospital and will be asked to report any adverse event or any untoward event to the research fellow. Patients will be also be inquired for any side effects during the phone call made 3 months after surgery.

⁷ Data will be collected through personal interview and through electronic medical records. Data will also be collected through the phone call made 3 months after surgery.

Pre-operative data collection:

1. Pain scores using numerical rating scores (NRS) during the pre-operative evaluation visit
2. Brief pain inventory (BPI) at pre-operative evaluation visit.
3. Demographic data to be obtained includes height (cm), weight (kg), age (yr.), gender, (ASA) physical status, and self-declared ethnicity.
4. Patients will be questioned for social history (tobacco) and medical history (pulmonary disease, kidney disease, diabetes mellitus, neurological disease, chronic pain conditions, illegal drug usage, alcohol abuse, myocardial infarction, previous surgery or stent placement and medications usage).
5. Available preoperative laboratory tests and medication list will be recorded.
6. Individual risk for nausea and vomiting will be determined using the Apfel score.

Post-operative data collection:

1. Pain scores using numerical rating scores (NRS):
 - a. Every 15 minutes for the first hour after surgery.
 - b. Every four hours after the first hour until 72 hours after the surgery.
2. Brief pain inventory (BPI) prior to hospital discharge or at 72 hours post op whichever comes first
3. The QoR-15 score to formally evaluate quality of recovery. The QoR-15 score is a validated scoring system allows quantification of patient's early postoperative health status, which is also a description of quality of recovery. The QoR-15 scoring will be done prior to hospital discharge or at 72 hours post op whichever comes first.

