7.2 Statistical Methods

The modified intention-to-treat approach will be utilized: patients who were randomized, had the procedure and received any amount of treatment will be included in the analysis. The per-protocol analysis (on patients who were randomized, had the procedure and followed the treatment regimen at least 50% of the times) will be conducted for the primary outcome as a sensitivity analysis.

First, randomized groups will be compared for balance on potentially confounding baseline demographic and preoperative variables using descriptive statistics.

Primary outcome. In the primary hypothesis, quality of postoperative analgesia will be characterized using both pain scores and total postoperative opioid consumption within 72 hours of the surgery or till discharge. We will consider gabapentin enacarbil group better than placebo group on the postoperative pain management if gabapentin enacarbil group is found noninferior (i.e., not worse) on both outcomes and superior on at least one of the outcomes. We define the a-priori noninferiority pain score delta as 1 point and the opioid delta as 1.1 for the ratio in geometric

means IV morphine equivalent doses (meaning 10% difference between group's median doses). Thus, our primary hypothesis will be assessed in a joint hypothesis-testing framework described by Mascha and Turan (42).

We will first estimate confidence intervals for the treatment effect for both pain score and opioid consumption. Assuming lognormal distribution of opioid consumption, we will evaluate the percent difference in geometric mean IV morphine equivalent dose between the two groups using a log-linear regression model. To evaluate the difference in mean pain scores we will first summarize the pain scores by computing time weighted average (TWA) pain score for each patient. Then we will use a linear regression model to assess the treatment effect on the TWA pain scores.

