Our joint hypothesis testing will consist of two steps. First, we will evaluate the noninferiority of gabapentin enacarbil to placebo group on both outcomes. Noninferiority (being “not worse”) of gabapentin enacarbil group will be concluded for both outcomes at the significance level of 0.025 if the upper limit of 95% confidence interval is below the corresponding noninferiority delta. Second, if noninferiority is concluded for both pain scores and opioid consumption, we will proceed to a 1-tailed superiority test on each outcome in the same direction as the noninferiority testing. Superiority testing will be done at the overall 0.025 significance level and will be adjusted for multiple testing (two outcomes) via Bonferroni correction ($0.025/2=0.0125$); superiority will thus be claimed for a particular outcome if the 97.5% confidence interval is below zero (below one for ratio in geometric means for opioid). Overall Type I error rate for the joint hypothesis testing will be maintained at 0.025 (we choose 0.025 instead of 0.05 because we have to consider treatment effect both directions gabapentin enacarbil vs. placebo and placebo vs. gabapentin enacarbil) even though both noninferiority and superiority will be tested at the 0.025 level. This is because noninferiority on both outcomes and superiority on at least one is required to claim gabapentin enacarbil group better than placebo group, and thus the joint hypothesis framework is an intersection-union test (which does not require additional adjustment for testing two sets of hypotheses).

In addition to the confidence intervals, tests giving the P-values for noninferiority and superiority will be performed. For noninferiority, two 1-tailed t-tests for each outcomes will be done to assess whether the difference in means pain scores (or ratio in geometric means for opioid) is below the given delta (log of given delta for opioid). For superiority, two 1-tailed t-tests will be done in the same direction as the noninferiority testing to assess whether the difference in means pain scores (or ratio in geometric means for opioid) is below zero (one). Estimates of treatment effect and standard error will be based on the regression models described above. .

Secondary outcomes. We will compare two randomized groups on each secondary outcome using appropriate 2-tailed tests for superiority: t-tests or Wilcoxon rank sum tests for continuous outcomes as of duration of hospitalization and QoR-15 satisfaction score.

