To assess if administration of gabapentin enacarbil decreases the incidence of nausea and vomiting within initial 72 hours of the surgery and the risk of pain conversion from acute to chronic chi-square tests will be used.

The significance level for the set of secondary outcomes will be preserved at 0.05 overall by using a criterion of $P < 0.05/4 = 0.0125$ for each test (applying a Bonferroni correction for multiple testing of the 4 secondary outcomes).

R statistical software version 2.12.1 (The R Foundation for Statistical Computing, Vienna, Austria)

and SAS statistical software version 9.3 (SAS Institute, Cary, NC, USA) for 64-bit Microsoft Windows will be used for all statistical analysis.

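### QoR-15, the Aim 4 endpoint, has no pre-operative score and an unadjusted analysis, which costs some precision but causes no bias

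*Combined protocol and SAP*

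**What the plan says.** Section 2 makes patient satisfaction Secondary Aim 4, a comparison with placebo "as assessed using the quality of recovery score (QoR-15"). Section 3.3 lists it as the fourth secondary endpoint.

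The score is taken once. Section 4.5 states: "The QoR-15 score will be performed on 72 hours post op or at discharge whichever comes first". Footnote 7 of section 6.4 gives the same single time point: "The QoR-15 scoring will be done prior to hospital discharge or at 72 hours post op whichever comes first". The pre-operative list in that footnote covers NRS pain, the BPI, demographics with ASA status, history, laboratory tests and medications, and the Apfel score. QoR-15 is not on it. The BPI is collected both before surgery ("Brief pain inventory (BPI) at pre-operative evaluation visit") and after it ("Brief pain inventory (BPI) prior to hospital discharge or at 72 hours post op whichever comes first"), but no objective, endpoint or test names it.

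For the analysis, section 7.2 plans two-tailed "t-tests or Wilcoxon rank sum tests for continuous outcomes as of duration of hospitalization and QoR-15 satisfaction score". The threshold for each test is 0.0125, "applying a Bonferroni correction for multiple testing of the 4 secondary outcomes". No covariate is given for any secondary outcome. Pre-operative variables have one stated use: the arms are "compared for balance on potentially confounding baseline demographic and preoperative variables using descriptive statistics".

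**The concern.** Patients awaiting hip or knee replacement plausibly differ in pain and general health before any study drug is taken. If part of that difference carries through to the score at discharge or 72 hours, a two-sample test on the post-operative value counts it as noise. A baseline score used as a covariate would remove that part.

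Aim 4 has little precision to spare, with 50 patients per arm and a two-sided threshold of 0.0125. The visit at which a baseline could be taken already exists and already carries two patient-reported pain measures. Section 7.1 also says that variability seen in this pilot may be used to plan a later study. Without a baseline QoR-15, the trial cannot estimate the correlation needed to size a later adjusted analysis.

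**Working it through.** **The plan's own figures.** The documents give no power, SD or target difference for QoR-15. The only power statement (section 7.1) is about 90% for opioid consumption. It reproduces: log-scale SD = √ln(1 + 0.7²) = 0.6315, |ln 0.63| = 0.4620, 50 per arm and one-sided 0.0125 give 91.5% by the noncentral t with 98 df. That figure does not bear on Aim 4. The secondary threshold also checks: 0.05/4 = 0.0125.

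**Inputs for Aim 4**
- From the documents: 50 per arm (section 7.1); two-sided 0.0125 (section 7.2).
- Assumed: the correlation r between baseline and post-operative QoR-15, taken as 0.2, 0.3 and 0.5; true differences of 0.5 SD and 0.65 SD.

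**Formulas (normal approximation)**
- Critical value: z = 2.4977 for two-sided 0.0125.
- Standard error of the difference in SD units, unadjusted: √(2/50) = 0.2.
- Adjusting for baseline multiplies residual variance by (1 − r²).
- Power ≈ Φ(d / (0.2·√(1 − r²)) − 2.4977).
- Difference detectable with 80% power: (2.4977 + 0.8416) × 0.2 × √(1 − r²).
- Equivalent total sample size: 100 / (1 − r²).

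**Worked lines for d = 0.65**
- Unadjusted: 0.65/0.2 = 3.25; 3.25 − 2.4977 = 0.752; Φ = 0.774.
- r = 0.2: 3.25/√0.96 = 3.317; 3.317 − 2.4977 = 0.819; Φ = 0.794.
- r = 0.3: 3.25/√0.91 = 3.407; 3.407 − 2.4977 = 0.909; Φ = 0.818.
- r = 0.5: 3.25/√0.75 = 3.753; 3.753 − 2.4977 = 1.255; Φ = 0.895.

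| Analysis | Residual variance | Equivalent N | Detectable at 80% power | Power at 0.5 SD | Power at 0.65 SD |
|---|---|---|---|---|---|
| Unadjusted, as planned | 1.00 | 100 | 0.67 SD | 50.1% | 77.4% |
| Adjusted, r = 0.2 | 0.96 | 104 | 0.65 SD | 52.1% | 79.4% |
| Adjusted, r = 0.3 | 0.91 | 110 | 0.64 SD | 54.9% | 81.8% |
| Adjusted, r = 0.5 | 0.75 | 133 | 0.58 SD | 65.1% | 89.5% |

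Using the t distribution with 97 df lowers the 0.5 SD column by under 2 points (48.5%, 50.5%, 53.2%, 63.4%) and leaves the pattern unchanged.

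**Two checks on the form of the change**
- Baseline collected but the planned test kept: the test ignores the baseline, so power at 0.5 SD stays at 50.1%.
- Change score instead of adjustment: the variance factor is 2(1 − r). At r = 0.3 it is 1.4 and power at 0.5 SD falls to 35.0%. At r = 0.5 it is 1.0 and power is 50.1%, no better than having no baseline.

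**The case against.** The other side has a good case. The protocol describes QoR-15 as a measure of early post-operative status and recovery, and Aim 4 claims a difference from placebo, not a change from baseline. A single post-operative comparison answers that question. Only the primary outcome is powered, in a fixed sample that the protocol calls a pilot. The size of any gain is assumed. The baseline would be taken one to two weeks before surgery by the calendar heading, or up to a month by its footnote, and the outcome follows within three days of arthroplasty. Nothing in the documents favours r = 0.5 over r = 0.2. At 0.2 the gain is trivial. The table also compares with no adjustment at all. Adjusting for the pre-operative NRS or BPI might capture part of the same gain, and how much more a baseline QoR-15 would add is not estimated.

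All of this stands, and it limits the point to an inexpensive improvement. It does not remove it, because section 7.2 specifies no covariate for QoR-15, so as written the trial uses neither a new baseline nor the ones it has.

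A reader might infer more than the documents support:
- *That Aim 4 cannot separate a drug effect from arms that differed at the start.* Allocation is randomized, concealed and stratified by surgery type (section 5.3). The comparison is unbiased, and the test's error rate already allows for chance imbalance.
- *That imbalance would be invisible.* NRS, BPI, ASA status, chronic pain and comorbidities are recorded before surgery, and section 7.2 compares the arms descriptively on pre-operative variables. Only imbalance on QoR-15 itself is unseen.
- *That the BPI is collected for nothing and could be dropped.* It has no endpoint or inferential analysis, but the pre-operative BPI can enter the balance comparison and serve as a covariate. Dropping it would discard a useful baseline.

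**Conclusion.** The point holds as one of efficiency on a secondary endpoint. QoR-15 is tested at two-sided 0.0125 from one post-operative score with no adjustment, so any variation carried over from before surgery stays in the error term. Aim 4 remains valid and unbiased.

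The gain forgone depends on a correlation that the documents do not give. It is small at r = 0.2 to 0.3 (2 to 5 points of power at 0.5 SD) and material at about r = 0.5 (15 points at 0.5 SD, 12 at 0.65 SD). If r is near zero, nothing is gained and almost nothing is lost. These figures assume 50 analysable patients per arm and a linear relation between baseline and outcome. The two target differences are illustrative, not taken from the plan. Priority is low.

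**What to change.** Make two edits together.

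1. Section 6.4, footnote 7: add QoR-15 to the pre-operative list, completed at the baseline/enrolment visit before randomization.
2. Section 7.2: compare QoR-15 with a linear model for the post-operative score on treatment, baseline QoR-15 and surgery type (the stratification factor), at the same 0.0125 threshold. Do not use a change score.

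If the extra form is not wanted, make only the section 7.2 edit, with the pre-operative NRS or BPI as the covariate in place of baseline QoR-15. Keep the pre-operative BPI in either case, and state its role as a balance variable and possible covariate.

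The cost is a few minutes per patient for a 15-item form at a visit that patients already attend, one sentence in section 7.2, and one degree of freedom for the baseline covariate (one more for surgery type), out of 98 in the planned two-sample t-test.

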6.5 Laboratory Procedures

No samples (e.g., blood, tissue, etc.) need to be shipped offsite for analysis. We will not perform any procedures or tests.

7. STATISTICAL PLAN

7.1 Sample Size Determination

Sample size is fixed to be at 100 patients. We will recruit 100 patients having hip or knee arthroplasties with spinal anesthesia. 50 patients control will be given the placebo for five days and 50 patients will be given GEn 600 mg bid for five days.

Power consideration. Sample size is fixed to be at 100 patients. Power estimation is based on the analysis of superiority on opioid consumption because this analysis requires more patients than the superiority analysis on pain scores. As it is stated in the hypothesis to claim positive effect of gabapentin enacarbil at least on one of these outcomes should be superior. Assuming the pilot study recruited total 100 patients and coefficient of variation (SD/mean) of 0.7 for both groups, we would have about 90% power to detect the ratio of 0.63 in geometric means in opioid consumption (i.e., a geometric mean opioid consumption decreases more than 37% in gabapentin enacarbil patients) comparing gabapentin enacarbil patients to patients receiving placebo at significance level of 0.0125.

If the assumptions appear to be too optimistic and study turns out to be underpowered, nevertheless treatment effects and variability identified in this pilot investigation can be used to plan a future study with sufficient power.

7.2 Statistical Methods

The modified intention-to-treat approach will be utilized: patients who were randomized, had the procedure and received any amount of treatment will be included in the analysis. The per-protocol analysis (on patients who were randomized, had the procedure and followed the treatment regimen at least 50% of the times) will be conducted for the primary outcome as a sensitivity analysis.

First, randomized groups will be compared for balance on potentially confounding baseline demographic and preoperative variables using descriptive statistics.

Primary outcome. In the primary hypothesis, quality of postoperative analgesia will be characterized using both pain scores and total postoperative opioid consumption within 72 hours of the surgery or till discharge. We will consider gabapentin enacarbil group better than placebo group on the postoperative pain management if gabapentin enacarbil group is found noninferior (i.e., not worse) on both outcomes and superior on at least one of the outcomes. We define the a-priori noninferiority pain score delta as 1 point and the opioid delta as 1.1 for the ratio in geometric

means IV morphine equivalent doses (meaning 10% difference between group's median doses). Thus, our primary hypothesis will be assessed in a joint hypothesis-testing framework described by Mascha and Turan (42).

We will first estimate confidence intervals for the treatment effect for both pain score and opioid consumption. Assuming lognormal distribution of opioid consumption, we will evaluate the percent difference in geometric mean IV morphine equivalent dose between the two groups using a log-linear regression model. To evaluate the difference in mean pain scores we will first summarize the pain scores by computing time weighted average (TWA) pain score for each patient. Then we will use a linear regression model to assess the treatment effect on the TWA pain scores.

Our joint hypothesis testing will consist of two steps. First, we will evaluate the noninferiority of gabapentin enacarbil to placebo group on both outcomes. Noninferiority (being “not worse”) of gabapentin enacarbil group will be concluded for both outcomes at the significance level of 0.025 if the upper limit of 95% confidence interval is below the corresponding noninferiority delta. Second, if noninferiority is concluded for both pain scores and opioid consumption, we will proceed to a 1-tailed superiority test on each outcome in the same direction as the noninferiority testing. Superiority testing will be done at the overall 0.025 significance level and will be adjusted for multiple testing (two outcomes) via Bonferroni correction ($0.025/2=0.0125$); superiority will thus be claimed for a particular outcome if the 97.5% confidence interval is below zero (below one for ratio in geometric means for opioid). Overall Type I error rate for the joint hypothesis testing will be maintained at 0.025 (we choose 0.025 instead of 0.05 because we have to consider treatment effect both directions gabapentin enacarbil vs. placebo and placebo vs. gabapentin enacarbil) even though both noninferiority and superiority will be tested at the 0.025 level. This is because noninferiority on both outcomes and superiority on at least one is required to claim gabapentin enacarbil group better than placebo group, and thus the joint hypothesis framework is an intersection-union test (which does not require additional adjustment for testing two sets of hypotheses).

In addition to the confidence intervals, tests giving the P-values for noninferiority and superiority will be performed. For noninferiority, two 1-tailed t-tests for each outcomes will be done to assess whether the difference in means pain scores (or ratio in geometric means for opioid) is below the given delta (log of given delta for opioid). For superiority, two 1-tailed t-tests will be done in the same direction as the noninferiority testing to assess whether the difference in means pain scores (or ratio in geometric means for opioid) is below zero (one). Estimates of treatment effect and standard error will be based on the regression models described above. .

Secondary outcomes. We will compare two randomized groups on each secondary outcome using appropriate 2-tailed tests for superiority: t-tests or Wilcoxon rank sum tests for continuous outcomes as of duration of hospitalization and QoR-15 satisfaction score.

To assess if administration of gabapentin enacarbil decreases the incidence of nausea and vomiting within initial 72 hours of the surgery and the risk of pain conversion from acute to chronic chi-square tests will be used.

The significance level for the set of secondary outcomes will be preserved at 0.05 overall by using a criterion of $P < 0.05/4 = 0.0125$ for each test (applying a Bonferroni correction for multiple testing of the 4 secondary outcomes).

R statistical software version 2.12.1 (The R Foundation for Statistical Computing, Vienna, Austria)

and SAS statistical software version 9.3 (SAS Institute, Cary, NC, USA) for 64-bit Microsoft Windows will be used for all statistical analysis.

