3. STUDY DESIGN

3.1 General Design

A randomized controlled trial to determine the effect of gabapentin enacarbil on opioid consumption and pain scores in patients having primary hip or knee replacement surgery with spinal anesthesia. Randomization will be web-based and stratified by type of surgery. Allocation will be concealed until shortly before drug/placebo administration.

Participating patients will be randomly assigned to standard management with GEN or to standard management with placebo. Patients will be given GEN 600 mg bid or placebo 600 mg bid for 1 preoperative day and will receive 600 mg GEN or placebo about 2 hours before surgery and then restarted on GEN or placebo 600 mg within 6 hours of surgery, and then 600 mg bid for three additional days.

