5.3 Method for Assigning Subjects to Treatment Regimen

Participating patients will be randomly assigned to gabapentin enacarbil or placebo. Randomization will be web-based through REDCap and stratified by type of surgery. Allocation will be concealed until shortly before drug/placebo administration. Randomization will be stratified by type of surgery (hip versus knee). Randomization codes will be web based using random-sized blocks, and treatment assignment (gabapentin enacarbil or placebo) will be done using a password-protected website administered by the Department of Outcomes Research statistical team at Cleveland Clinic.

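### Neither primary model names a covariate, although randomization is stratified by hip/knee and preoperative pain is collected; prespecifying both terms would add precision at almost no cost

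*Combined protocol and SAP*

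**What the plan says.** Section 7.2 (Statistical Methods) describes the opioid analysis as follows: "we will evaluate the percent difference in geometric mean IV morphine equivalent dose between the two groups using a log-linear regression model". For time-weighted average (TWA) pain it says: "Then we will use a linear regression model to assess the treatment effect on the TWA pain scores". Neither sentence lists a model term other than treatment. The same section then ties the noninferiority and superiority tests to these models: "Estimates of treatment effect and standard error will be based on the regression models described above". The tests themselves are described as "two 1-tailed t-tests for each outcomes will be done to assess whether the difference in means pain scores" lies below the margin, with parallel tests for superiority.

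The only use Section 7.2 gives to baseline data is descriptive: "First, randomized groups will be compared for balance on potentially confounding baseline demographic and preoperative variables using descriptive statistics".

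Elsewhere, Section 3.1 states: "Randomization will be web-based and stratified by type of surgery". Section 5.3 repeats this and identifies the strata as hip and knee. Footnote 7 of the Section 6.4 calendar lists, among the preoperative data, "Pain scores using numerical rating scores (NRS) during the pre-operative evaluation visit". Section 7 uses neither variable in a primary analysis.

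**The concern.** The sample is fixed at 100 (Section 7.1), so extra precision cannot come from recruitment. Every primary decision is a confidence bound or one-sided t-test from these two models: noninferiority on both outcomes at 0.025, then superiority on each at 0.0125.

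A treatment-only model can give away precision in two separate ways.

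- **Surgery type.** Stratified randomization balances hip and knee between arms, so the treatment estimate already has the smaller, within-stratum variance. A treatment-only standard error still counts the between-stratum variance as noise. It is therefore too large, the intervals over-cover and the tests are conservative.
- **Preoperative NRS.** This variable is not balanced by design. The treatment-only interval is correctly calibrated but wider than it needs to be if NRS predicts the outcome.

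There is also a matter of prespecification. A regression with no listed terms, alongside a balance check on possible confounders, leaves room to choose covariates after the data are seen.

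**Working it through.** **Inputs from the documents.** 50 patients per arm; CV 0.7; target ratio of geometric means 0.63; superiority one-sided at 0.0125; noninferiority one-sided at 0.025; margins 1.1 (opioid ratio) and 1 point (pain).

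**Assumed, because the documents give no value.** The share of outcome variance explained by the covariates (R² 0.10 and 0.25) and its source; the hip/knee opioid ratio (1.2, 1.5, 2.0) and surgery mix (50:50, 30:70); the SD of TWA pain (1.5, 2, 2.5).

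**1. The plan's own power.** Log-scale variance V = ln(1 + 0.7²) = 0.3988, so SD = 0.6315. SE = 0.6315 × √(2/50) = 0.1263. Noncentrality = |ln 0.63| / 0.1263 = 0.4620 / 0.1263 = 3.66. The noncentral t with 98 df at one-sided 0.0125 gives 91.5%. The stated figure of about 90% therefore reproduces without any covariate.

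**2. Size of the test when the stratum is omitted.** The share of log-dose variance due to surgery type is R²s = p(1 − p)(ln ratio)² / V, where p is the proportion in one stratum. With p = 0.5:
- ratio 1.2: 0.25 × 0.0332 / 0.3988 = 0.021
- ratio 1.5: 0.25 × 0.1644 / 0.3988 = 0.103
- ratio 2.0: 0.25 × 0.4805 / 0.3988 = 0.301

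With balance within strata, the estimate has variance V(1 − R²s) × 2/50. The pooled residual variance, scaled by 98 / [V(1 − R²s)], is noncentral chi-square with 98 df and noncentrality 100·R²s/(1 − R²s). Numerical integration gives the true size:

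| Knee/hip ratio | Nominal 0.025, 50:50 | Nominal 0.025, 30:70 | Nominal 0.0125, 50:50 |
|---|---|---|---|
| 1.2 | 0.0238 | 0.0240 | 0.0118 |
| 1.5 | 0.0192 | 0.0201 | 0.0090 |
| 2.0 | 0.0095 | 0.0117 | 0.0037 |

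**3. Power, treatment-only versus treatment + surgery type + NRS.** The adjusted model uses the noncentral t with 96 df and standard error SE × √[(1 − R²)/(1 − r²)], averaged over chance NRS imbalance r² ~ Beta(1/2, 97/2). Adjusted power depends only on total R². Treatment-only power also depends on the source of R², because the design already captures the surgery-type part.

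| Test | Source of R² | R² 0.10 | R² 0.25 |
|---|---|---|---|
| Opioid superiority, ratio 0.63 | NRS | 91.5 → 93.9% | 91.5 → 97.2% |
| | surgery type | 92.5 → 93.9% | 94.2 → 97.2% |
| Opioid superiority, ratio 0.75 | either | about 50 → 54.6% | about 50 → 63.3% |
| Opioid noninferiority, ratio 0.80 | NRS | 70.4 → 74.5% | 70.4 → 81.8% |
| | surgery type | 71.3 → 74.5% | 73.0 → 81.8% |
| Opioid noninferiority, ratio 1.0 | NRS | 11.3 → 12.0% | 11.3 → 13.5% |
| | surgery type | 10.0 → 12.0% | 8.0 → 13.5% |
| Pain noninferiority, no difference, SD 2 | NRS | 69.7 → 73.7% | 69.7 → 81.1% |
| | surgery type | 70.6 → 73.7% | 72.2 → 81.1% |

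For pain SD 1.5 and 2.5 with R² 0.25 from NRS, noninferiority power moves from 91.0 to 96.6% and from 50.8 to 62.3%.

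**4. Cost if the covariates explain nothing.** Superiority at 0.63 goes from 91.46 to 91.15%; superiority at 0.75 from 50.29 to 49.80%; noninferiority at 0.80 from 70.43 to 69.96%; noninferiority at 1.0 from 11.26 to 11.19%. The loss is 0.1 to 0.5 point.

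**5. Simulation.** With surgery-type R² 0.25, 100,000 simulated trials per scenario gave size 0.0118 treatment-only and 0.0249 adjusted (nominal 0.025), and superiority power at 0.63 of 94.3% and 97.3%. Separate runs of 20,000 trials with permuted blocks found mean estimates within 0.002 of the true log ratio in every setting.

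**The case against.** The plan is valid as it stands. Omitting a prognostic stratum errs on the conservative side, which is the safe direction for noninferiority tests. The size of the gain cannot be taken from the documents. R² of 0.25 from surgery type alone needs a 1.88-fold opioid difference (50:50 mix). From NRS it needs a correlation of 0.50 with a score that Section 4.3 allows to be up to a month old at surgery. At the plan's own design point (ratio 0.63), opioid noninferiority power is already 99.2%, and R² of 0.10 adds only 1.4 to 2.4 points to superiority power. The larger gains arise at ratios or pain SDs that the plan does not state. Power for the joint criterion was not computed. The word regression could also be meant to include covariates, and NRS is one of several baseline variables that could have been chosen.

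Most of this stands, and it limits the point to a minor one. It does not remove it. If the models are meant to be adjusted, Section 7.2 must name the terms; if they are meant to be treatment-only, it should say so and accept the conservatism. The surgery-type term follows from the randomization, whatever its prognostic strength. The NRS term is a judgment, better supported for pain than for opioid dose. Section 7.1 offers the pilot's variability for planning a later study, but that adds little to the argument, because a residual SD can be computed from the same data later.

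**Conclusion.** The concern holds as a minor one: a possible gain in precision is left unused, and the primary models are not fully specified. There is no bias and no type I inflation, and the stated power does not depend on adjustment.

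The gain depends on how prognostic the two covariates are, which the documents do not say. Over the assumed R² range of 0.10 to 0.25 it is about 1 to 6 points for superiority at the design ratio, and about 3 to 11 points for noninferiority at a true opioid ratio of 0.80 or with a pain SD of 2. It is negligible if surgery type shifts opioid use only 1.2-fold and NRS is uninformative.

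Adjustment does not ease the strict 1.1 opioid margin. With no true difference, noninferiority power stays below about 14% for R² up to 0.25, with or without the covariates.

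**What to change.** In Section 7.2, before unblinding:

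- Specify both primary models (log opioid dose and TWA pain) as treatment + surgery type (hip/knee) + preoperative NRS, with no optional covariates.
- State that all primary confidence intervals and all one-sided noninferiority and superiority tests come from these models.
- Keep patients with a missing preoperative NRS in the modified intention-to-treat set by imputing the overall baseline mean.
- Report the treatment-only model as a sensitivity analysis.

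If the team prefers treatment-only as primary, Section 7.2 should say so explicitly and acknowledge that the tests are conservative if surgery type predicts outcome.

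The cost is a few added sentences, 2 degrees of freedom, and at most about half a power point if the covariates explain nothing. No new data are needed.
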